6.2.2.1.4 Intra-subject Dose Escalation

In Part 1, certain subjects who enroll in the study and receive the full planned dose for at least 2 cycles will be allowed to receive a higher dose of tarlatamab once such dose is deemed safe by DLRT. Both the medical monitor and PI must deem it safe before a subject is considered for intra-subject dose escalation. The subject must be informed of the potential risks and benefits. Intra-subject dose escalation should only occur if the subject experienced \leq Grade 1 toxicity during the previous course. If any cases of Grade \geq 3 toxicity occur at the current or any previous lower dose levels, no intra-patient dose escalation should be allowed at that dose level. See Section 8.1.2 for more details on the changes regarding the schedule of activities for subjects who undergo intra-subject dose escalation.

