6.2.2.1.1 Dosage Adjustment

Subjects should continue on the same target dose of tarlatamab (not including the initial run-in dose and step dose(s)) throughout the study. The two exceptions are subjects who meet criteria for intra-subject dose escalation (see Section 6.2.2.1.4 for more details) and subjects who experienced a DLT or other intolerable tarlatamab-related adverse events but showing evidence of clinical benefit. These subjects will have an option to reduce the dose to the immediate next lower dose level shown to be safe and tolerable in the dose exploration part of the study, after discussion with the Amgen Medical Monitor. The study drug can be resumed once the adverse events recover to Grade 0-1 and the reintroduction of tarlatamab is deemed safe by the investigator, Medical Monitor, and GSO. The subjects must be informed of the risk of continuing on therapy. Each subject is only allowed one dose reduction. For adverse events related to CRS, neurological events, and pituitary dysfunction, please see Sections 6.8.1, 6.8.2, and 6.8.3, respectively for guidelines for dose adjustments.

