6.8 Support Care and Potential Risk Management Guidelines for Tarlatamab

6.8.1 Cytokine Release Syndrome (CRS)

CRS is clinically defined and may have various manifestations. There are no established diagnostic criteria. Signs and symptoms of CRS may include (Lee et al, 2014):

- **Constitutional:** fever \pm rigors, fatigue, malaise, myalgias, anorexia, arthralgias, nausea, vomiting, headache

- **Neurologic:** headache, mental status changes, confusion, delirium, word finding difficulty or frank aphasia, hallucinations, tremor, dysmetria, altered gait, seizures
- **Respiratory:** dyspnea, tachypnea, hypoxemia
- **Cardiovascular:** tachycardia, hypotension, widened pulse pressure, increased cardiac output (early), potentially diminished cardiac output (late)
- **Gastrointestinal:** nausea, vomiting, diarrhea
- **Renal:** azotemia
- **Hepatic:** transaminitis, hyperbilirubinemia
- **Hematology/Coagulation:** hypofibrinogenemia ± bleeding, elevated D-dimer
- **Skin:** rash

CRS is an identified risk of tarlatamab administration. Subjects may be at an increased risk for CRS during the first few days following the initial infusion of tarlatamab and after a dose step increase. CRS may be life-threatening or fatal. Infusion reactions may be clinically indistinguishable from manifestations of CRS. Subjects will be hospitalized for intensive monitoring for 48 hours post tarlatamab infusion during all cycle 1 doses (refer to Section 8.1.2 for hospitalization guidance). Throughout the infusion with tarlatamab and at least 4 hours after the end of infusion, monitor subjects intensively for clinical signs (eg, fever, hypotension, tachycardia, dyspnea, tremors) and laboratory changes (eg, transaminase increase) which may be related to CRS.

Grading and management of CRS should be performed according to the guidelines provided in Table 6-2 (Lee et al, 2014). For subjects with suspected CRS, samples may be collected for analysis after discussion with the Medical Monitor.

Table 6-2. Grading and Management of Cytokine Release Syndrome

CRS Grade	Description of Severity ^a	Minimum Expected Intervention	Instructions for Dose Modifications of Tarlatamab

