8.1.2 Treatment Period

Treatment begins on cycle 1 day 1 when the first IV infusion of investigational product is administered to a subject. The study procedures to be completed during the treatment period are designated in the Schedule of Activities (Section 1.3).

The results of the cycle 1 day 1 laboratory tests must be available before starting treatment with tarlatamab. Laboratory assessments that were done within 24 hours prior to infusion do not need to be repeated, except for cycle 1 day 1 dosing where laboratory assessments should be collected within 4 hours before cycle 1 day 1 dosing of tarlatamab. Clinical evaluation should be completed within 6 hours prior to the first dose of tarlatamab.

All assessments and procedures should be collected at the exact nominal time point as noted in the Schedule of Activities. If unable to perform a procedure at the specified nominal time point, collect it as close as possible to the nominal time point and record the actual collection time.

The EOT visit will occur at the end of the last treatment cycle. For subjects who prematurely discontinue IP treatment, the EOT visit should occur as soon as possible after the last dose of investigational product was administered.

Hospitalization Guidance

All subjects will be hospitalized for intensive monitoring for 48 hours post tarlatamab infusion during all cycle 1 doses. Hospitalization is not required for cycle 2 unless a subject experiences grade 2 or higher CRS or neurological events in cycle 1 (minimum of 24 hours hospitalization required post tarlatamab infusion on C2D1 if grade 2 or higher CRS or neurological events are noted in cycle 1). The subjects may be

discharged after this period if there are no signs and symptoms of cytokine release syndrome or other acute toxicities.

Study sites must have immediate access to a medical intensive care unit staffed by critical care providers.

If subjects are not hospitalized during cycle 2, subjects will be observed for 8 hours post tarlatamab infusion.

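### The protocol promises a changed schedule after intra-subject dose escalation, but Section 8.1.2 and the visible Schedule of Activities contain none, so the first higher dose falls under routine cycle 3+ rules (minor)

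*Protocol*

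**What the plan says.** Protocol 6.2.2.1.4 allows a higher dose for certain Part 1 subjects who have had at least 2 cycles at the full planned dose, once the Dose Level Review Team (DLRT) has judged that dose safe. The medical monitor and the investigator must both agree. The section adds a toxicity condition: "Intra-subject dose escalation should only occur if the subject experienced" nothing worse than grade 1 in the previous course. Any grade 3 or higher toxicity at the current or a lower level closes escalation at that level. It ends: "See Section 8.1.2 for more details on the changes regarding the schedule of activities for subjects who undergo intra-subject dose escalation".

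The permission is live. Section 6.2.2.1.1 keeps subjects on one target dose and then states: "The two exceptions are subjects who meet criteria for intra-subject dose escalation", alongside subjects who reduce the dose for toxicity.

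Section 8.1.2 covers the start of treatment, pre-dose tests, nominal times, the end-of-treatment visit and hospitalization. Its periods belong to named cycles:
- Cycle 1: "All subjects will be hospitalized for intensive monitoring for 48 hours post tarlatamab infusion during all cycle 1 doses".
- Cycle 2, day 1: "minimum of 24 hours hospitalization required post tarlatamab infusion on C2D1 if grade 2 or higher CRS" or neurological events occurred in cycle 1.
- Cycle 2 otherwise: "If subjects are not hospitalized during cycle 2, subjects will be observed for 8 hours post tarlatamab infusion".

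It does not mention intra-subject escalation, and it shows no blacked-out text.

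Section 6.8.1 says subjects may be at "increased risk for CRS during the first few days following the initial infusion of tarlatamab and after a dose step increase". It asks for intensive monitoring during the infusion and for at least 4 hours afterwards.

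**The concern.** The sponsor's own sentence shows that a changed schedule was intended. A site that follows the reference finds nothing and falls back on the rules for the cycle the subject is in. Those rules were relaxed from cycle 3 on the footing that the subject is already established on the dose. A first exposure to a higher target dose does not fit that footing.

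Elsewhere the protocol does address CRS at late dosing. Section 6.8.4 asks sites to consider hospitalization when treatment restarts after a COVID-19 interruption, partly because of CRS risk, even at the same or a lower dose. Table 6-2 links same-dose continuation after grade 3 CRS to dexamethasone premedication. A late dose increase has no comparable instruction.

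What is at stake is safety cover at one infusion per escalated subject, and consistency between sites in how that infusion is observed. The safety data are not lost: adverse events after an escalated dose still reach the DLRT.

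**Working it through.** The documents give no figure to reproduce. The check sets the stated rules side by side and then counts the subjects who could be affected.

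**1. When the first higher dose falls.** At least 2 cycles at the full planned dose must come first (6.2.2.1.4), so it falls in cycle 3 or later.

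**2. What is required by cycle** (SoA footnotes e, r, s; 6.8.1; 8.1.2):

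| Measure | Cycle 1 | Cycle 2 | Cycle 3 onward |
|---|---|---|---|
| Dexamethasone 8 mg IV | before every dose | not required | not required |
| 1 L normal saline | after every dose | not required | not required |
| Stay or observation | 48 h inpatient | at least 24 h on day 1 after grade 2 or higher CRS or neurological events in cycle 1; 8 h if not hospitalized | at least 4 h intensive monitoring (6.8.1) |
| Timed vital signs after infusion | footnote e grid to 24 h | footnote e grid, to 8 h if not hospitalized | institutional practice |

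**3. What still applies at cycle 3 or later.** Table 1-2 keeps clinical evaluation, vital signs with pulse oximetry, blood count, coagulation, chemistry, CRP and ferritin on days 1 and 15. ECGs before and after infusion continue in cycles 3 and 4 (footnote y). Table 6-2 applies in any cycle: once grade 1 CRS is recognized, vital signs and oximetry are due at least every 2 hours for 12 hours or until resolution.

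**4. Gap against the nearest comparator.** A subject in cycle 2 who is not hospitalized is observed for 8 h; the escalated dose has a floor of 4 h. The difference is 8 - 4 = 4 h. From hour 2 after the end of infusion to hour 8, the footnote e grid has 5 readings (2, 2.5, 3, 3.5, 4 h) plus 4 (5, 6, 7, 8 h) = 9, of which 4 fall after hour 4. From cycle 3 none of these times is fixed by the protocol.

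**5. Reach.**
- Lower bound: 0. Part 1 is dropped if the small cell lung cancer study has already selected the recommended dose (4.1). The SAP's relative dose intensity formula (5.1) also assumes a single 1-to-100 mg regimen, and 100 mg is the highest first-in-human (FIH) monotherapy dose reported (2.2.2.3).
- Upper bound: Part 1 has up to 20 subjects. The DLRT recommends no escalation with fewer than 3 evaluable subjects at a level (6.2.1.1). If clearing the higher dose also takes 3 subjects treated there, at most 20 - 3 = 17 remain. If it takes the 6 that 4.1 uses for safe and tolerable, 20 - 6 = 14 remain.
- The grade 3 bar lowers this further. As an illustration only, take the FIH incidence of grade 3 or higher treatment-emergent events (48.6%) and assume independent subjects. A level of 3 has no such event with probability 0.514^3 = 14%, and a level of 6 with 0.514^6 = 2%. At half that rate (24.3%), the values are 0.757^3 = 43% and 0.757^6 = 19%. The FIH rate is all-cause, so the true closing rate may be lower.

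**The case against.** The strongest reply is that this is a dangling cross-reference with little behind it. Several parts of that reply stand.

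- **Gatekeeping and rescue are real.** The DLRT, medical monitor and investigator must clear the dose, and recent toxicity must be mild. Tocilizumab or siltuximab is on site (6.1.4), and 8.1.2 adds: "Study sites must have immediate access to a medical intensive care unit staffed by critical care providers". The sponsor may change dexamethasone (6.1.3) and the DLRT may change premedication (Appendix 3). These measures decide who escalates, allow case-by-case direction or treat an event. None states a premedication or observation period for the escalated dose.
- **The CRS argument is partly extrapolation.** The risk sentence in 6.8.1 is written around step dosing. In the FIH study CRS came mainly after the first 2 doses in cycle 1 and typically did not recur (2.2.2.3). The documents give no CRS rate for a late dose increase, so no added risk can be quantified or excluded.
- **Some material cannot be seen.** Hidden SoA footnotes or the IPIM may contain instructions. The finding is therefore limited to the visible text, although the reference itself goes to 8.1.2.

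A reader might measure the 4 h floor against the 24 h and 48 h stays and call the whole difference a shortfall. The documents do not support that. The 48 h stay was set for cycle 1 doses, and the 24 h stay for subjects with grade 2 or higher events in cycle 1. The nearest comparator for other subjects is 8 h.

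**Conclusion.** The point holds as a minor defect. A current permission relies on a schedule that 8.1.2 and the visible SoA do not contain. Followed as written, the first higher dose at cycle 3 or later has routine visit assessments and at least 4 h of intensive monitoring, with no required dexamethasone, hydration or longer observation.

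Two stronger readings should be avoided. Subjects would not go unmonitored, because the routine cycle 3+ assessments and the CRS management table still apply. Nor is all of Part 1 exposed: 0 to about 17 subjects could be affected, and the grade 3 bar makes the top of that range unlikely.

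This rests on two assumptions. The 4 h sentence in 6.8.1 is taken to apply in every cycle; read as cycle 1 only, no explicit minimum would remain. The bound of 17 assumes that clearing the higher dose uses at least 3 evaluable subjects at that level.

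**What to change.** In 8.1.2 and one SoA footnote, require for the first escalated dose:
- dexamethasone 8 mg IV within 1 hour before the infusion;
- 1 L normal saline after it;
- at least the existing cycle 2 protection: 8 h observation with the footnote e vital signs, or a 24 h stay if the subject had grade 2 or higher CRS or neurological events in cycle 1.

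Leave the DLRT free to require 24 h or 48 h when it clears the dose.

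If escalation is no longer intended, delete the permission in 6.2.2.1.4 and the matching exception in 6.2.2.1.1.

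The first option costs one paragraph and one footnote, and for each escalated subject one steroid dose, one saline infusion and a longer observation period. The second costs two deletions.

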6.2.3 Hepatotoxicity Stopping and Rechallenge Rules

Refer to Section 11.7 for details regarding drug-induced liver injury guidelines, as specified in the *Guidance for Industry Drug-Induced Liver Injury: Premarketing Clinical Evaluation, July 2009*.

6.3 Preparation/Handling/Storage/Accountability

Guidance and information on preparation, handling, storage, accountability, destruction, or return of the investigational product during the study are provided in the IPIM.

6.4 Measures to Minimize Bias: Randomization and Blinding

6.4.1 Method of Treatment Assignment

Subjects who meet eligibility criteria will be assigned to treatment with tarlatamab.

6.4.2 Blinding

This is an open-label study; blinding procedures are not applicable.

6.5 Treatment Compliance

Compliance with treatment and the corresponding assessments should be followed according to the Schedule of Activities (Section 1.3) and the Treatment Procedures (Section 8.2). Refer to the IPIM for additional information.

6.6 Treatment of Overdose

The effects of overdose of this product are not known. **The administered investigational product dose may be up to 10% lower or higher than specified in**

the protocol. A dose of up to 10% higher than the intended dose may not require specific intervention.

In any case of overdose, consultation with the Amgen Medical Monitor is required for prompt reporting of clinically apparent or laboratory adverse events possibly related to overdosage. Consultation with the Amgen Medical Monitor is also required even if there are no adverse events, in order to discuss further management of the subject. If the overdose results in clinically apparent or symptomatic adverse events, the subject should be followed carefully until all signs of toxicity are resolved or returned to baseline and the adverse event(s) should be recorded/reported as per Section 11.4.

A dose of > 10% higher than the intended investigational product dose will be considered clinically important and classified as a serious adverse event under the criterion of “other medically important serious event” (See Section 11.4).

6.7 Prior and Concomitant Treatment

6.7.1 Prior Treatment

Prior therapies that were being taken/used from 1 month prior to signing informed consent will be collected. For all prior therapies not taken for prostate cancer, collect therapy name, indication, dose, unit, frequency, route, start and stop dates.

For all prior therapies taken for prostate cancer (eg, chemotherapy or hormonal therapy), collect (in the order they were administered):

- therapy name
- indication
- dose and schedule of the agent(s)
- unit
- frequency
- start and stop dates
- disease state in which it was administered
- type of progression (biochemical [ie, a rising radiographic, and/or symptomatic)
- response (resistant versus sensitive): categorized on the basis of the post-therapy or radiographic change pattern for agents that reduce tumor burden

NOTE: A taxane regimen is defined as a minimum exposure of 2 cycles of a taxane.

Additionally, details of the dates, portals, and total administered dose by portal should be recorded for all courses of radiation therapy, including those directed at the primary and metastatic site(s). Details of prior radioisotope therapy should also be recorded.

6.7.2 Concomitant Treatment

Throughout the study, investigators may prescribe any concomitant medications or treatments deemed necessary, including the use of growth factors such as erythropoiesis-stimulating proteins as well as granulocyte colony stimulating factor (G-CSF), to provide adequate supportive care except for those listed in Section 6.1.6.

Concomitant therapies are to be collected from signing of the informed consent through the end of SFU period. For concomitant therapies being taken for the disease under study (eg, steroids, chemotherapy), collect therapy name, dose, unit, frequency, start date and stop date. For all other concomitant therapies, including vaccines collect therapy name, indication, dose, unit, frequency, route, start date and stop date, and record in the electronic case report form (eCRF).

6.7.3 Vaccines

Every effort should be made to fully vaccinate patients prior to 14 days from first dose of IP. The use of vaccines except live and live-attenuated vaccines will be allowed during therapy per regional and institutional standard of care. However, SARS-COV2 vaccinations should be avoided during screening (within a minimum of 14 days from first dose of IP) and should be also avoided in the first treatment cycle for better assessment of safety parameters. Throughout the trial, SARS-COV2 vaccination should be avoided within 3 days after the administration of IP. In the event where a patient requires steroids for treatment of AEs, vaccination should be avoided while on steroids. **Live and live attenuated vaccines can be used at least 60 days after the last dose of tarlatamab.**

6.8 Support Care and Potential Risk Management Guidelines for Tarlatamab

6.8.1 Cytokine Release Syndrome (CRS)

CRS is clinically defined and may have various manifestations. There are no established diagnostic criteria. Signs and symptoms of CRS may include (Lee et al, 2014):

- **Constitutional:** fever \pm rigors, fatigue, malaise, myalgias, anorexia, arthralgias, nausea, vomiting, headache

- **Neurologic:** headache, mental status changes, confusion, delirium, word finding difficulty or frank aphasia, hallucinations, tremor, dysmetria, altered gait, seizures
- **Respiratory:** dyspnea, tachypnea, hypoxemia
- **Cardiovascular:** tachycardia, hypotension, widened pulse pressure, increased cardiac output (early), potentially diminished cardiac output (late)
- **Gastrointestinal:** nausea, vomiting, diarrhea
- **Renal:** azotemia
- **Hepatic:** transaminitis, hyperbilirubinemia
- **Hematology/Coagulation:** hypofibrinogenemia ± bleeding, elevated D-dimer
- **Skin:** rash

CRS is an identified risk of tarlatamab administration. Subjects may be at an increased risk for CRS during the first few days following the initial infusion of tarlatamab and after a dose step increase. CRS may be life-threatening or fatal. Infusion reactions may be clinically indistinguishable from manifestations of CRS. Subjects will be hospitalized for intensive monitoring for 48 hours post tarlatamab infusion during all cycle 1 doses (refer to Section 8.1.2 for hospitalization guidance). Throughout the infusion with tarlatamab and at least 4 hours after the end of infusion, monitor subjects intensively for clinical signs (eg, fever, hypotension, tachycardia, dyspnea, tremors) and laboratory changes (eg, transaminase increase) which may be related to CRS.

Grading and management of CRS should be performed according to the guidelines provided in Table 6-2 (Lee et al, 2014). For subjects with suspected CRS, samples may be collected for analysis after discussion with the Medical Monitor.

Table 6-2. Grading and Management of Cytokine Release Syndrome

CRS Grade	Description of Severity ^a	Minimum Expected Intervention	Instructions for Dose Modifications of Tarlatamab
1	Symptoms are not life threatening and require symptomatic treatment only, eg, fever, nausea, fatigue, headache, myalgias, malaise	Administer symptomatic treatment (eg, paracetamol/acetaminophen for fever). Monitor for CRS symptoms including vital signs and pulse oximetry at least Q2 hours for 12 hours or until resolution, whichever is earlier.	N/A
2	Symptoms require and respond to moderate intervention 
 • Oxygen requirement <40%, OR • Hypotension responsive to fluids or low dose of one vasopressor, OR Grade 2 organ toxicity or grade 3 transaminitis per CTCAE criteria	Administer: 
 • Symptomatic treatment (eg, paracetamol/acetaminophen for fever) • Supplemental oxygen when oxygen saturation is < 90% on room air • Intravenous fluids or low dose vasopressor for hypotension when systolic blood pressure is < 85 mmHg. Persistent tachycardia (eg >120 bpm) may also indicate the need for intervention for hypotension. Monitor for CRS symptoms including vital signs and pulse oximetry at least Q2 hours for 12 hours or until resolution to CRS grade ≤ 1, whichever is earlier. For subjects with extensive co-morbidities or poor performance status or if CRS does not resolve to grade ≤ 1 in 48 hours, manage per grade 3 CRS guidance below.	If CRS occurs during tarlatamab treatment, immediately interrupt the infusion and delay the next tarlatamab dose until the event resolves to CRS grade ≤ 1 for no less than 72 hours. Resume tarlatamab at same dose or reduce to next lower dose, if clinically indicated (continuation with the next planned dose may be allowed after discussion with the Amgen Medical Monitor). Permanently discontinue tarlatamab if there is no improvement to CRS ≤ grade 1 within 7 days.

Footnotes defined on last page of table

Page 1 of 2

Table 6-2. Grading and Management of Cytokine Release Syndrome (CRS)

CRS Grade	Description of Severity ^a	Minimum Expected Intervention	Instructions for Dose Modifications of Tarlatamab
3	
Symptoms require and respond to aggressive intervention
 
 • Oxygen requirement $\geq 40\%$, OR • Hypotension requiring high dose^b or multiple vasopressors, OR 
Grade 3 organ toxicity or grade 4 transaminitis per CTCAE criteria
	
Admit to intensive care unit for close clinical and vital sign monitoring per institutional guidelines.
 
Administer dexamethasone (or equivalent) IV at a dose maximum of 3 doses of 8 mg (24 mg/day). The dose should then be reduced step-wise.
 
Investigators should consider use of tocilizumab^{c,d} 8 mg/kg over 1 hour (not to exceed 800 mg). Repeat tocilizumab^{c,d} every 8 hours as needed if not responsive to IV fluids or increasing supplemental oxygen. Maximum of 3 doses in a 24-hour period. Maximum total of 4 doses.
 
If tocilizumab is not available, siltuximab (an anti-IL-6 monoclonal antibody) may be used. The recommended dose of siltuximab is 11 mg/kg administered over 1 hour as an intravenous infusion, consistent with the prescribing information for the treatment of multicentric Castleman's disease (Sylvant Prescribing Information), and the CARTOX Working Group Guidelines for CRS management (Neelapu et al, 2018). Siltuximab may be repeated if needed, in the event that CRS recurs after a subsequent infusion of tarlatamab. Siltuximab may not be repeated in an individual subject who develops anaphylaxis to siltuximab, or gastrointestinal perforation after siltuximab.
 
Investigators may also consider additional therapy, based on clinical judgment.
	
If CRS occurs during tarlatamab treatment, immediately interrupt tarlatamab and delay the next dose until event resolves to CRS grade ≤ 1 for no less than 72 hours.
 
Resume tarlatamab to next lower dose (continuation at same dose with dexamethasone premedication may be allowed after discussion with the medical monitor).
 
Permanently discontinue tarlatamab if there is no improvement to CRS \leq grade 2 within 5 days or CRS \leq grade 1 within 7 days.
 
Permanently discontinue tarlatamab or reduce to the next lower dose if CRS grade 3 occurs at the initial run in dose (ie, at MTD1) (applicable only after MTD1 has been defined).

CRS Grade	Description of Severity ^a	Minimum Expected Intervention	Instructions for Dose Modifications of Tarlatamab
4	Life-threatening symptoms 
 Requirement for ventilator support OR Grade 4 organ toxicity (excluding transaminitis) per CTCAE criteria 	
Admit to intensive care unit for close clinical and vital sign monitoring per institutional guidelines. Administer dexamethasone (or equivalent) IV at a dose maximum of 3 doses of 8 mg (24 mg/day). Further steroid use should be discussed with the Amgen medical monitor. Investigators should consider use of tocilizumab^{c,d} 8 mg/kg IV over 1 hour (not to exceed 800 mg). Repeat tocilizumab^{c,d} every 8 hours as needed if not responsive to IV fluids or increasing supplemental oxygen. Maximum of 3 doses in a 24-hour period. Maximum total of 4 doses.
 
If tocilizumab is not available, siltuximab (an anti-IL-6 monoclonal antibody) may be used. The recommended dose of siltuximab is 11 mg/kg administered over 1 hour as an intravenous infusion, consistent with the prescribing information for the treatment of multicentric Castleman's disease (Sylvant Prescribing Information), and the CARTOX Working Group Guidelines for CRS management (Neelapu et al, 2018). Siltuximab may be repeated if needed, in the event that CRS recurs after a subsequent infusion of tarlatamab. Siltuximab may not be repeated in an individual subject who develops anaphylaxis to siltuximab, or gastrointestinal perforation after siltuximab.
 
Investigators may also consider additional therapy, based on clinical judgment.
	
If CRS occurs during tarlatamab treatment, immediately stop the infusion. Permanently discontinue tarlatamab therapy.

^a Revised grading system for CRS (Lee et al, 2014)

^b High dose vasopressors (all doses are required for ≥ 3 hours): Norepinephrine monotherapy ≥ 20 µg/min; Dopamine monotherapy ≥ 10 µg/kg/min, Phenylephrine monotherapy ≥ 200 µg/min, Epinephrine monotherapy ≥ 10 µg/min; If on vasopressin, vasopressin + norepinephrine equivalent of ≥ 10 µg/min; If on combination vasopressors (not vasopressin), norepinephrine equivalent of ≥ 20 µg/min

^c If tocilizumab is not available, siltuximab (an anti-interleukin-6 [IL-6] monoclonal antibody) may be used in the management of cytokine release syndrome, following the criteria outlined in the Management of Adverse Events table. The recommended dose of siltuximab is 11 mg/kg administered over 1 hour as an intravenous infusion, consistent with the prescribing information for the treatment of multicentric

Castleman's disease (Sylvant Prescribing Information), and the CARTOX Working Group Guidelines for CRS management (Neelapu, 2018). Siltuximab may be repeated if needed, in the event that CRS recurs after a subsequent infusion of tarlatamab. Siltuximab may not be repeated in an individual subject that develops anaphylaxis to siltuximab, or gastrointestinal perforation after siltuximab.

^d A subgroup analysis for subjects treated with siltuximab will be evaluated, including CRS outcomes, safety, and PK data.

Re-start of treatment after CRS:

After a grade 2 or 3 CRS event, the next infusion may be administered if all of the following criteria are met:

- The Amgen medical monitor must be consulted prior to re-starting treatment
- If CRS occurred during tarlatamab infusion, infusion has been interrupted for at least 72 hours
- The event has resolved to grade ≤ 1 prior to re-starting treatment

If a subject experiences two separate grade 3 CRS events, tarlatamab must be permanently discontinued.

